**GOLD Grade 1-4 at Screening**

Subjects will be classified into Global Initiative on Obstructive Lung Disease (GOLD) Grades 1-4 using the post-salbutamol percent predicted FEV1 assessment at Screening:

- GOLD Grade 1 (Mild): percent predicted FEV1  $\geq$  80%
- GOLD Grade 2 (Moderate): 50%  $\leq$  percent predicted FEV1  $<$  80%
- GOLD Grade 3 (Severe): 30%  $\leq$  percent predicted FEV1  $<$  50%
- GOLD Grade 4 (Very Severe): percent predicted FEV1  $<$  30%

**Death**

Details of any patient deaths, including date of death, will be recorded in the CRF. Information will be obtained from the telephone interview and from medical records in HIS. Cause of death will be recorded if available. Data from publicly available source will be used if participant is not contactable at the end of the study.

**Blood Biomarker**

- Blood samples will be taken at Visit 1 and throughout the study as defined in the time and events table. ([Appendix 2: Schedule of Activities](#)).
- Plasma fibrinogen, hsCRP, total/differential blood cell count measurements and haemoglobin will be conducted at central lab for all participants
- Additional protein analysis will be conducted at central lab for the sub-cohort using validated assays. Analytes chosen will include serum sRAGE, CC16 and IP-10, HbA1c.
- The blood biomarker assessments will be conducted according to the study reference manual.

**Sputum Microbiome and Sputum Cytology**

- Sputum samples for microbiome and sputum cytology will be collected at Visit 1 and Visit 4 in sub-cohort only as defined in the time and events table ([Appendix 2: Schedule of Activities](#)).
- Sputum can be collected spontaneously or can be induced, as per investigator judgement, induced sputum is preferred. Sputum sampling should only be done if, in the opinion of the investigator, it is safe for the subject. The sputum microbiome and sputum cytology assessments will be conducted according to the sputum assessment procedure (Refer to study reference manual).

**Sputum Microbiome and Sputum Cytology**

- Additional analyses may include the measurement of viruses and fungi.

CCI

**COPD-related Healthcare Resource Utilization**

Within site hospital COPD-related healthcare resource utilization and cost will be captured on the study questionnaire form where possible using the HIS (based on site feasibility). Information collected include:

- Unscheduled COPD outpatient visits and emergency visits
  - Number of visits, date of visit, diagnosis of visit, cost
- COPD hospitalization (including intensive care)
  - Number of hospitalizations, date and length of stay, diagnosis of visit, cost
- Prescribed COPD medications
  - Medication name, date of prescription, dosage, administration, cost, whether the prescription is picked up at hospital, etc.
- Other COPD treatment, e.g. oxygen therapy, nebulizers
  - Treatment name, date, cost, etc.
- Lab tests, image tests, surgeries, and other tests and procedures (e.g., spirometry, Chest X-Ray, CT)
  - Test or procedure, date of operation, cost, etc.
- Healthcare cost if feasible, e.g. general service usage, consultation fee
  - Item, date of charge
- Insurance coverage and patient out-of-pocket payment if feasible

Additionally, healthcare resource utilization could occur in other places outside of the site hospitals including: (1) hospitals other than the site hospital where the subject is recruited; (2) retail pharmacy stores; (3) subjects' home.

Outside of site hospital COPD-related healthcare resource utilization and cost will be collected using standard questionnaires at trimonthly subjects' phone interviews. Information collected include COPD-related diagnosis and treatment in the following sources:

- Outpatient visit, emergency visit, and hospitalization

### COPD-related Healthcare Resource Utilization

- Date, reason, length of stay (for hospitalization)
- Prescribed medications
- Over-the-counter (OTC) medications
- Other therapies, e.g. oxygen therapy, nebulizers
- Associated costs if feasible
- Lab tests, image tests, surgeries, and other tests and procedures (e.g., spirometry, Chest X-Ray, CT)

### Adverse Events

Adverse Events (AE) will not be captured in the study as no study drug will be given in this study.

- If an AE (serious or non-serious) or complaint with any specifically named GSK product is reported spontaneously by a subject during the course of the study, the site staff will complete the AE reporting form and transmit the report to the GSK China within 24 hours of being made aware of the AE.

Study procedure related serious adverse events (SAE) will be recorded.

- All SAEs will be collected from the signing of the ICF until the follow-up visit at the time points specified in the Schedule of Activities ([Appendix 2: Schedule of Activities](#))
- The investigator is responsible for the detection and documentation of events meeting the criteria and definition of an SAE, provided in this protocol. During the study when there is a safety evaluation, the investigator or site staff will be responsible for detecting, documenting, and reporting SAEs

Serious Adverse Event (SAE) is defined as any untoward medical occurrence that:

- Results in death,
- Is life-threatening,
- Requires hospitalization or prolongation of existing hospitalization,
- Results in disability/incapacity,
- Is a congenital anomaly/birth defect,
- Other: medical or scientific judgement should be exercised in deciding whether reporting is appropriate in other situations, such as important medical events that may not be immediately life-threatening or result in death or hospitalization but may jeopardize the subject or may require medical or surgical intervention to prevent one of the other outcomes listed in the above definition. These should also be considered serious.
- Possible drug-induced liver injury

See study Pharmacovigilance Plan (sPVP) for details. sPVP will include the following elements to ensure a comprehensive approach to safety event collection and reporting:

- Supplier pharmacovigilance training
- Investigator and site staff pharmacovigilance training
- Safety-specific roles

Adverse Events

• SAEs collection and reporting processes

• SAEs collection forms

• Frequency of data review

• Reporting process and timelines

• Interim reports

• Study-specific PVP monitoring process

### **17.5.3. Patient-reported Outcome**

CAT

• The CAT is an 8-item questionnaire suitable for completion by all patients diagnosed with COPD. When completing the questionnaire, participants rate their experience on a 6-point scale, ranging from 0 (no impairment) to 5 (maximum impairment) with a scoring range of 0-40. Higher scores indicate greater disease impact.

• For all participants, CAT will be completed at baseline, each follow up clinic visit, and tri-monthly phone interviews. Interviewer-administered approach (face-to-face or over the phone) will be used.

• Additionally, for monitoring purpose, monthly CAT will be interviewer-administered over phone call in the sub-cohort for 6 months after baseline visit and 6 months after Visit 3. CAT will also be assessed in the sub-cohort at exacerbation visits.

CAPTURE

• The CATPURE is a short, five-item questionnaire that can be easily completed by patients and are used to identify individuals who may have undiagnosed, clinically significant COPD.

• The algorithm is a simple summation of patient responses to each of the five items. (For Question 1-4, Score 0 for No, Score 1 for Yes, Question 5, Score 0,1,2. So the total score is ranging from 0 to 6). Higher score means higher risk of COPD (0-1 is at low risk, 2-6 is at high risk).

St. George's Respiratory Questionnaire for COPD Patients (SGRQ-C)

• The SGRQ-C contains 14 questions with a total of 40 items grouped into three domains (Symptoms, Activity and Impacts).

• The details for how to score the SGRQ-C are outlined in the SGRQ-C manual (Jones, 2016). This includes details on how to handle missing data.

• SGRQ-C domain and total score will be converted to SGRQ scores as described in the manual.

• The converted SGRQ scores will be used for all summaries/analyses.

**mMRC Dyspnea Scale**

- The modified Medical Research Council (mMRC) Dyspnea Scale quantifies disability attributable to breathlessness and is useful for characterizing baseline dyspnea in patients with respiratory diseases.
- mMRC is a simple one-item questionnaire that is completed by patients to grade their degree of baseline functional disability due to dyspnea. The 5 options in the question item translate to a 0-4 score range, with higher score indicating higher severity.

**EXACT and E-RS:COPD**

- The EXACT is a 14-item daily diary designed to provide a measure of patient-reported symptoms of COPD exacerbation. An EXACT Total Score, ranging from 0 to 100, where higher scores indicate a more severe condition, will be derived for each day of diary collection according to the instructions in the EXACT User Manual (Version 4.0, Evidera, 2011).
- Definition of EXACT events: magnitude of responder for symptomatic events defined as acute, sustained symptomatic worsening of COPD, defined as an increase in EXACT score  $\geq 9$  points for 3 days or  $\geq 12$  points for 2 days, above baseline (average in 7-day period)
- The EXACT daily diary will be completed each evening electronically for a month following Visit 1 and Visit 3.
- The E-RS™ involves the use of 11 of the 14 EXACT-PRO™ items and a different scoring algorithm to assess the severity of respiratory symptoms in patients with COPD. The E-RS™ score ranges from 0 to 40 with higher scores indicating more severe symptoms.
- Three subscales of the E-RS: COPD are used to describe different symptoms: breathlessness, cough and sputum, and chest symptoms.
- EXACT and E-RS score's scoring algorithms are from the EXACT-PRO user manual (Evidera, 2011).

Scale	Item-level Construct	Item Number	Score Range
RS-Breathlessness			
	Breathless today	7	0-4
	Breathless with activity	8	0-3
	Short of Breath – personal care	9	0-4
	Short of Breath – indoor activity	10	0-3
	Short of Breath – outdoor activity	11	0-3
RS-Cough and Sputum			
	Cough frequency	2	0-4
	Mucus quantity	3	0-3
	Difficulty with mucus	4	0-4
RS-Chest Symptoms			
	Congestion	1	0-4
	Discomfort	5	0-4
	Tightness	6	0-4
Respiratory Symptoms	E-RS Total	11 items	0-40

EXACT and E-RS:COPD			
Additional Attributes			
Used in the EXACT total score for characterizing exacerbations, specifically	Tired or weak	12	0-4
	Sleep disturbance	13	0-4
	Scared or worried	14	0-3
EXACT – Exacerbation	EXACT Raw Total Score 	14 items	0-55

EXACT Total Score will be transformed to a 0-100 scale based on the raw total score

### Exact Event

Definition of EXACT events: magnitude of responder for symptomatic events defined as acute, sustained symptomatic worsening of COPD, defined as an increase in EXACT score  $\geq 9$  points for 3 days or  $\geq 12$  points for 2 days, above baseline (average in 7-day period).

### Clinically important deterioration (CID)

Clinically important deterioration (CID) is a new composite outcome (developed by GSK) for the prediction of future risk of long-term adverse outcomes. The definition of composite CID used in this study is CAT-CID:

- Occurrence of a moderate/severe exacerbation and/or
- $\geq 100$  mL deterioration from baseline in postbronchodilator FEV1 and/or
- $\geq 2$  units deterioration in the CAT.

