### **9.2.5. Clinically important deterioration (CID) components**

Clinically important deterioration (CID) is a new composite outcome (developed by GSK) for the prediction of future risk of long-term adverse outcomes. In this study, the CID will be derived from three key clinical assessments, which are 1) count of moderate/severe exacerbations, 2) worsening of FEV1, and 3) change in the CAT score measured over 6 months. CID was defined as: decrease of  $\geq 100$  mL in post-bronchodilator FEV1, or increase of  $\geq 2$  units in the CAT, or an occurrence of a moderate/severe exacerbation.

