#### 10.1.2. Study Design Considerations

This is a longitudinal study in subjects with COPD and controls. The follow-up period is 2.5 years with scheduled clinic visits at study entry, 6 months, 18 months, and 30 months.

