#### 10.1.3. Sample size Considerations

Sample size was decided based on practical consideration; however, some justification of GOLD I and II Grades and for sample size for all COPD patients is provided below.

There is no formal inference planned, meaning no powered hypothesis test for overall study will be performed. Sample size justification is based on precision of effect estimates for rate of decline in FEV1 over 2.5 years.

A review of data from Study HZC113782 FEV1 was collected at 3-month intervals on moderate COPD subjects suggests that a within subject standard deviation (model based residual error estimate) as 155 mL, and a standard error of the rate of decline in FEV1 as 2.5 mL/year from placebo group. Those variability estimates were increased to 50% higher as 233 mL and 3.8 mL/year, respectively, for the following sample size calculation; this is mainly based on the consideration that a more heterogeneous study population and non-drug interventional cohort nature by design will yield higher variability comparing to those observed in a randomized clinical trial.

To make simple calculation, it is assumed within subject's standard deviation and standard error of the rate of decline in control groups (Chronic Bronchitis, Healthy Control) are the same as the assumption for COPD subjects.

To detect a difference of  $\Delta$  units between the mean rate of decline in two groups, Schlesselman [Schlesselman, 1973] proposed the following formula to calculate  $N$ ,

$$N = [2(Z_{\alpha/2} + Z_{\beta})^2 \{\hat{\sigma}_{\beta}^2 + 12(P-1)\hat{\sigma}^2/[D^2P(P+1)]\}]/\Delta^2$$

where  $\hat{\sigma}_{\beta}^2$  is an estimate of the variance associated with the rate of decline in FEV1,  $\hat{\sigma}^2$  is an estimate of the variation about the regression line within a person,  $D$  is the duration of the study,  $P$  is the number of measurements collected during the study,  $Z_{\alpha/2}$  is the upper  $(1 - \alpha/2)$  critical value for the standard normal distribution, and  $Z_{\beta}$  is the upper  $(1 - \beta)$  critical value for the standard normal distribution. It can be adapted to determine  $N$  for a

$100(1 - \alpha)\%$  two-sided confidence interval for the difference between the rates of decline in  $FEV_1$  of two groups that has precision  $\Delta$  as

$$N_1 = Z_{\alpha/2}^2 \hat{\sigma}_p^2 (r + 1) / (r \Delta^2)$$

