### 2.2.1. Additional information for endpoints of COPD progression

#### Exacerbation (Chapter 7)

Times of exacerbation 0-18m (baseline to Month 18, same for the followings) and 0-30m will be summarised. Rate of exacerbation (yearly) will be estimated based on negative binomial distribution at the end of study.

CID and its components are defined in [7.2](#). Percentage of participants who have any event(s) in 0-6m, 6-18m, 18-30m will be presented.

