## 7.2. Clinically Important Deterioration (CID)

Clinically Important Deterioration (CID) is a new composite outcome (developed by GSK) for the prediction of future risk of long-term adverse outcomes. CID components are defined as:

- Exacerbation: An occurrence of a moderate/severe exacerbation.
- FEV1: Decrease of  $\geq 100$  mL in postbronchodilator FEV1
- CAT: Increase of  $\geq 2$  units in the CAT

CID event, or CID-positive (CID+) is considered as to have ANY of the 3 components.

A summary of participants in Full population who had at least 1 CID event in Baseline to Month6, Month6 to Month18 and Month18 to Month30 will be provided, the occurrence of CID and the components will be summarised. Considering the Spirometry onsite test may delay due to COVID, an additional rule of analysis window for post-baseline FEV1 is defined as planned visit date  $\pm 90$  days. If there's no available record, the result will be regarded as missing (no event).

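### CID is reported for three separate intervals, but the only stated FEV1 reference is baseline and CAT has no clear one, so the later columns cannot be read as deterioration in that period

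*SAP*

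**What the plan says.** SAP section 2.2.1 sets the display: "Percentage of participants who have any event(s) in 0-6m, 6-18m, 18-30m will be presented". Section 7.2 repeats it for participants with "at least 1 CID event in Baseline to Month6, Month6 to Month18 and Month18 to Month30". Neither section restricts an interval to new events, removes participants who are already CID-positive, or calls the columns cumulative.

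The component definitions do not agree on what change is measured from:

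- **FEV1, SAP 7.2:** a decrease of at least 100 "mL in postbronchodilator FEV1", with no reference point.
- **FEV1, SAP 17.5.3:** at least 100 mL "deterioration from baseline in postbronchodilator FEV1".
- **FEV1, Protocol 9.2.5:** the same 100 mL threshold, with no reference point.
- **CAT, SAP 7.2 and 17.5.3:** a worsening of at least 2 units, with no reference point.
- **CAT, Protocol 9.2.5:** "change in the CAT score measured over 6 months".
- **Exacerbation:** the occurrence of a moderate or severe event, which belongs to the interval in which it happens.

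Section 7.2 also sets a window of 90 days either side of the planned visit for post-baseline FEV1 and treats an unavailable value as no event.

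**The concern.** An exacerbation in 18-30 months is something that happened in 18-30 months. FEV1 at Month 30 at least 100 mL below Visit 1 is a state, and the loss may date from any time in the preceding 30 months. Combining the two under interval headings gives a percentage that is neither an interval rate nor a cumulative one. A participant who lost 150 mL by Month 6 and then stayed level is FEV1-positive, and so CID-positive, in all three columns although nothing new happened after Month 6.

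The alternative reading, change within each interval, fits the headings of 2.2.1 and 7.2 but contradicts 17.5.3. Two programmers could each follow part of the SAP and produce different tables. For CAT the gap is wider: the protocol's 6-month span fits only the first interval, because the other two last 12 months.

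Frequency of CID and its components is a listed main-cohort progression endpoint, so readers will try to read the three columns as a course over time.

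**Working it through.** The documents state no expected CID rate, so there is no CID figure to reproduce. The calculation below only gives the size of the gap between the two readings.

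**Inputs**

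- Visit times of 0, 0.5, 1.5 and 2.5 years: "scheduled clinic visits at study entry, 6 months, 18 months, and 30 months" (Protocol 10.1.2). Each CID interval therefore has one scheduled closing FEV1.
- Within-person SD: "a within subject standard deviation (model based residual error estimate) as 155 mL" (Protocol 10.1.3), raised there by 50% to 233 mL for planning.
- Mean decline d: not given in the documents. Assumed 40 mL/year, range 0-60.
- Model (assumed): linear decline with independent normal visit errors of SD s.

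**Formulae**

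The difference between two visits has SD s × √2: 155 × 1.414 = 219.2 mL, or 233 × 1.414 = 329.5 mL.

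- Positive against baseline at time t: Φ((d × t − 100) / (s√2)).
- Positive from the start of the 18-30-month interval, which lasts one year: Φ((d − 100) / (s√2)).
- The Month 0-30 and Month 18-30 differences share the Month 30 error, so their correlation is 0.5. The bivariate normal probability that both reach 100 mL gives the share of Month 30 positives with no such drop in the last interval: 1 − P(both) / P(positive at Month 30).

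**Worked at d = 40, s = 155**

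- Month 6: Φ((20 − 100) / 219.2) = Φ(−0.365) = 36%.
- Month 18: Φ((60 − 100) / 219.2) = Φ(−0.182) = 43%.
- Month 30: Φ((100 − 100) / 219.2) = Φ(0) = 50%.
- Month 18-30, interval start: Φ((40 − 100) / 219.2) = Φ(−0.274) = 39%.
- P(both) = 0.276, so 1 − 0.276 / 0.500 = 44.8%.

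**Results**

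| s (mL) | d (mL/yr) | Month 6 / 18 / 30 against baseline | 18-30 from interval start | Month 30 positives with no observed 100 mL drop in 18-30 |
|---|---|---|---|---|
| 155 | 0 | 32 / 32 / 32% | 32% | 45.8% |
| 155 | 40 | 36 / 43 / 50% | 39% | 44.8% |
| 155 | 60 | 38 / 48 / 59% | 43% | 43.9% |
| 233 | 0 | 38 / 38 / 38% | 38% | 41.6% |
| 233 | 40 | 40 / 45 / 50% | 43% | 40.9% |
| 233 | 60 | 42 / 49 / 56% | 45% | 40.3% |

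A simulation of 2 million participants agrees at d = 40: 44.9% (s = 155) and 40.9% (s = 233).

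**How often a Month 6 event is counted three times.** At d = 40, about 51% of Month 6 FEV1 positives are positive at all three visits, with either SD.

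**The case against.** The defence has real substance. The study is descriptive with no formal inference, the components are shown separately, and FEV1 change and slope are analysed without CID. Baseline is a legitimate reference: the superseded RAP bound with the SAP measured FEV1 and CAT from baseline and reported CID status at Visits 2, 3 and 4, which is coherent. On that view only a label is wrong. This limits the importance of the point but does not remove it. The current SAP uses interval headings, keeps the baseline wording in one place, and omits any reference in the section that drives the table.

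Four stronger readings are tempting, and the documents do not support them.

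- **Every early loss is counted three times.** This holds only for a loss that persists, which is about half of Month 6 positives in the model at 40 mL/year.
- **The baseline rule manufactures a rising FEV1 trend.** With zero decline it is flat (32% at all three visits, SD 155). The rise to 50% is the assumed cumulative loss of 20, 60 and 100 mL, which a status against baseline ought to show.
- **The baseline rule misses real drops in 18-30 months.** In the model each participant's true loss in that year equals the assumed decline, at most 60 mL. The observed 100 mL drops need measurement error to reach the threshold, so the figures compare two noisy differences and say nothing about true deterioration missed.
- **A single figure of 45%.** That needs the uninflated SD of 155 mL and an assumed decline. The planning SD of 233 mL gives about 41%.

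Measuring from the start of each interval is not clearly better either. In the same model it flags 39-43% in 18-30 months at 40 mL/year. It also needs two in-window FEV1 values, so under the rule in 7.2 a missed Month 18 visit could make both the 6-18 and the 18-30-month intervals non-events.

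**Conclusion.** The point holds as an inconsistency that leaves the CID table undefined for FEV1 and CAT. If 17.5.3 is followed, the later columns combine new exacerbations with FEV1 losses of any date and cannot be read as deterioration in that period.

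Over an assumed decline of 0-60 mL/year and SDs of 155-233 mL, roughly 40-46% of observed Month 30 FEV1 positives have no observed 100 mL drop since Month 18. At 40 mL/year the choice of reference moves the last FEV1 column from about 50% to 39-43%, a gap of 7 to 11 percentage points. These sizes rest on an assumed decline, linear change and independent visit errors. They describe observed values for the FEV1 component alone.

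Separately, the intervals last 6, 12 and 12 months, so at a constant positive exacerbation rate that component is higher in the second column than in the first because of length alone. The documents give no rate from which to size this.

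**What to change.** State one reference for FEV1 and CAT, in the same words, in SAP 7.2 and 17.5.3, and label the table to match. Carry the same labels into 2.2.1. Either of two options is coherent:

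1. **Keep baseline.** Present cumulative CID at 0-6, 0-18 and 0-30 months, with exacerbations counted over the same spans.
2. **Use the visit that opens each interval.** Measure FEV1 and CAT from V1 to V2, V2 to V3 and V3 to V4, with exacerbations counted between the same visits. Report a participant lacking either in-window FEV1 value as not evaluable for that component, in place of the present no-event rule.

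If interval columns are kept, footnote that they last 6, 12 and 12 months. Say also how the protocol's 6-month CAT wording is to be applied.

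The cost is SAP wording and a small amount of programming, with no new data. Option 2 leaves fewer evaluable participants, and the table should show how many.
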